3.2.2 BASELINE/RANDOMIZATION (VISIT 2)

At the end of the 30-day lead-in period, subjects will return to the study site for visit 2. Eligibility criteria will be reviewed, including review of the EMA data during the lead-in period. If study participant meets eligibility based on review of baseline assessments, then subjects will be randomized and receive the first dose of erenumab or placebo.

Assessments to be performed during visit 2:

1. Concomitant medication review
2. Physical exam
3. Vital signs, height and weight
4. Pregnancy test (urine) if applicable
5. Review of data from EMA with instructions for continued use
6. Randomization
7. Administration of placebo or IP

Subjects will be given a portable home blood pressure monitoring device. Instructions for use of this device will be provided at the time of the first dose of the study drug. Subjects will record their blood pressure every day for seven consecutive days after the first dose. Thereafter, they will record their blood pressure once per week and when symptomatic throughout the entire duration of the study. Subjects will enter their blood pressure information through redcap or twilio. This data will be reviewed monthly by the PI or within 24 hours if immediate intervention is required. In addition, patients will be educated on the symptoms of high blood pressure and, at any time in the study, if symptomatic, the patient should check their blood pressure and notify the study coordinator. The coordinator may call the subject to remind them to record their blood pressure during their study participation.

For patients with normal baseline blood pressure (at or below 120/80), if subjects find that their blood pressure equals or exceeds 140 mm Hg systolic or 90 mm Hg diastolic on two consecutive readings within thirty minutes, they will notify the study coordinator and seek medical attention. For patients who have abnormal baseline blood pressure, if subjects find that their blood pressure equals or exceeds 160 mm Hg systolic or 100 mm Hg diastolic on two consecutive readings within 30 minutes, they will notify the study coordinator and seek medical attention. Subjects will be asked to repeat the pressure the following day. If persistently elevated for three consecutive days, subject will be removed from the study and referred for evaluation and treatment.

If a blood pressure is found to be greater than or equal to *180 mm Hg systolic or 120 mm Hg diastolic, and confirmed on a second measurement within 30 minutes, subjects will seek medical attention immediately. In addition to weekly monitoring, subjects will be instructed to measure their blood pressure immediately if they develop any symptoms associated with hypertensive crisis, such as chest pain, shortness of breath, headache, numbness/weakness, change in vision, difficulty speaking, confusion, or nausea/vomiting.* Subjects who develop hypertensive crisis at any point during the study will be removed from the study.

3.2.3 STUDY VISITS 3 THROUGH 7

During the treatment period, subjects will return to the study site every 30 days (+/- 6 days) and will undergo assessments and procedures listed in the schedule of events in section 1.3. Subjects will complete the patient-oriented outcome questionnaires noted in the schedule of events. Study medication (erenumab or placebo) will be administered per protocol. A review of the EMA data and concomitant medications (including over the counter medications) between each visit will occur. Subjects will be reminded to continue to record their symptom severity and rescue medicine intake each day through their mobile phone or via paper if not feasible. Subjects will also be reminded to continue blood pressure monitoring weekly and when symptomatic. The coordinator may call the subject to remind them to record their daily diary and blood pressure.

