3.2.4 FOLLOW-UP/END OF STUDY VISIT (VISIT 8)

Subjects will be asked to return for follow-up one month after the last study drug administration and undergo assessments and procedures listed in the schedule of events in section 1.3. Daily symptom and rescue medication data logs will be reviewed, and questionnaires completed. However, the study drug/placebo will not be administered.

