6.2 PARTICIPANT DISCONTINUATION/WITHDRAWAL FROM THE STUDY

Subjects will have the option of withdrawing from the study at any time for any reason. Reason and date for withdrawal, as well as any adverse events and concomitant medications since the last study visit will be documented.

The Principal Investigator may discontinue a subject from study treatment, or withdraw a patient from the study. Reasons for study treatment discontinuation or withdrawal may include but are not limited to the following:

- Adverse event or hypersensitivity reactions thought to be related to study drug (rash, angioedema, anaphylaxis, hypertensive crisis, persistently elevated blood pressure, constipation with serious complications).
- Patient voluntarily decides to withdraw.
- Patient non-compliance with the study protocol.
- Intercurrent disease, which in the opinion of the patient's treating physician, would affect the ability of the patient to continue on the clinical study.
- Patient lost to follow-up.

All subjects who received at least one dose of study drug or placebo will be requested to complete Visit 8, regardless of whether they completed the study, were withdrawn by the investigator or chose to withdrawal from the study.

Withdrawn and/or discontinued patients will be included in the data analysis by an intention to treat analysis.

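### Section 3.2.2 removes blood-pressure cases from the study rather than from study drug, and nothing clearly keeps their daily diary going through months 4-6

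*Combined protocol and SAP*

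**What the plan says.** **Removal rules.** Section 3.2.2 sets home blood-pressure thresholds and states: "If persistently elevated for three consecutive days, subject will be removed from the study and referred for evaluation and treatment". It adds: "Subjects who develop hypertensive crisis at any point during the study will be removed from the study". Both rules end study participation, not only dosing.

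**General withdrawal clause.** Section 6.2 is discretionary: "The Principal Investigator may discontinue a subject from study treatment, or withdraw a patient from the study". Its non-exhaustive list of reasons includes adverse events thought to be drug-related, among them "hypertensive crisis, persistently elevated blood pressure, constipation with serious complications".

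**Follow-up after stopping.** Section 6.2 says "All subjects who received at least one dose of study drug or placebo will be requested to complete Visit 8". Section 9.1.2 promises every effort at follow-up and a final visit in person or by phone. The schedule of events (Section 1.3) marks diary review and instruction at Visit 8 and at unscheduled visits. Section 3.2.4 says of Visit 8: "Daily symptom and rescue medication data logs will be reviewed, and questionnaires completed".

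**Timing of Visit 8.** Sections 1.3, 3.1 and 3.5 place the final visit at Day 180. Section 3.2.4 says: "Subjects will be asked to return for follow-up one month after the last study drug administration".

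**Analysis.** Section 6.2 commits that "Withdrawn and/or discontinued patients will be included in the data analysis by an intention to treat analysis", and Section 8.4.1 repeats the intention-to-treat principle. Section 8.4.2 specifies a linear mixed model without imputation and names no sensitivity analysis. Section 6.3 anticipates 10% dropout.

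**The concern.** The safety purpose of the blood-pressure rules is met by stopping the injections and referring the subject. Ending study participation goes further and puts outcome data at risk. The primary endpoint counts days scored above 4/10 in months 4-6 (Section 1.4), and those scores come from the daily diary (Section 7.1). A single visit or call cannot rebuild 90 days of daily scores.

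Removal may well come early. Section 2.3.1 says that most post-marketing hypertension cases began after the first dose, and Section 3.2.2 monitors most closely in the following week. A subject removed then can have nothing in the primary window.

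The mixed model would still use that subject's earlier months, but months 4-6 would in effect be inferred from subjects in the same arm who stayed in follow-up. That relies on the data being missing at random. Nothing planned tests this, whatever the cause of the missing data.

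**Working it through.** **1. The plan's own figure.** Inputs from Section 8.2: effect 3.0 days, SD 3.5, two-sided 0.05, power 90%, dropout 10%.

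- Normal approximation: n = 2 × (1.960 + 1.282)² × 3.5² / 3.0² = 28.6, so 29 per arm. 29 / 0.9 = 32.2, so 33, which matches.
- The exact t calculation needs 30 per arm (power 0.904).
- Starting from 30 against 30, losing 1 to 6 more in the erenumab arm leaves power at 89.9% to 86.7%. Power is not the issue.

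**2. Coverage of the primary window.** Read months 4-6 as Days 91-180. Dose k falls on Day 30(k − 1). If Visit 8 is one month after the last dose (Section 3.2.4) and the diary runs until then:

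| Last dose | Given on Day | Visit 8 on Day | Days covered, of 90 |
|---|---|---|---|
| 1 | 0 | 30 | 0 |
| 2 | 30 | 60 | 0 |
| 3 | 60 | 90 | 0 |
| 4 | 90 | 120 | 30 |
| 5 | 120 | 150 | 60 |
| 6 | 150 | 180 | 90 |

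The visit window adds at most 6 days (6 after dose 3, 36 after dose 4). If Visit 8 is at Day 180 instead, the window stays open, but it is filled only if the subject goes on making entries, and no section clearly asks for that.

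**3. Size of the shift.** The documents give no blood-pressure removal rate, so 1 to 3 removed erenumab subjects is an assumption. Planning standard error: 3.5 × √(2/33) = 0.862. Let x be the number of erenumab subjects removed before Day 90, and L the days of benefit each loses relative to staying on drug. Leaving out their later data shifts the estimate by about L × x / 33. A positive value means the benefit is overstated.

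| L (assumed) | x = 1 | x = 2 | x = 3 |
|---|---|---|---|
| 3 (all benefit lost) | 0.09 | 0.18 | 0.27 |
| 1.5 (half lost) | 0.05 | 0.09 | 0.14 |
| 0 (benefit replaced by a new drug) | 0 | 0 | 0 |
| −1 (ends 1 day better than on drug) | −0.03 | −0.06 | −0.09 |

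For L = 3, dividing by 0.862 gives 0.11, 0.21 and 0.32 standard errors.

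A simulation of a first-order autoregressive model with the baseline covariate (assumed correlation 0.7, 400 runs) agrees. With 3 removed after month 2 and L = 3, the estimate is −3.02 without the post-removal diary and −2.75 with it. With L = −1 the two are −2.97 and −3.06.

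**4. Could it change the conclusion?** Suppose 10% of the erenumab arm is missing from any cause.

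- A penalty of 1, 2 or 3 days per missing subject moves −3.0 to −2.9, −2.8 or −2.7.
- With 30 per arm the smallest significant difference is about 1.81 days (2.00 × 3.5 × √(2/30)).
- The penalty needed to lose significance is therefore (3.0 − 1.81) / 0.10 = 11.9 days, about four times the assumed effect.

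**The case against.** The strongest reply is that the point is immaterial on its own figures and that the plan is more careful than it looks. Several parts of that reply stand.

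- **Contradiction.** A reader might infer that Sections 3.2.2 and 6.2 contradict each other, since one says *will* and the other *may*. They do not, strictly. Section 6.2 is a general, non-exhaustive clause whose adverse-event item covers events thought to be drug-related. Section 3.2.2 sets specific thresholds that apply whatever the cause. A specific mandatory rule can sit inside a general discretionary one.
- **Zero coverage.** A reader might infer that a subject stopped at doses 1-3 necessarily has no primary-window data. The 0-of-90 result holds only on the Section 3.2.4 timing of Visit 8. Sections 1.3, 3.1 and 3.5 point to Day 180.
- **Efficacy dataset.** A reader might infer that early removals also fall out of the Section 8.3 efficacy dataset. That needs the diary to stop at once. If it runs for a month after dose 1, the subject can have a month-1 value and qualify.
- **Diary silence.** Section 3.2.2 gives instructions for continued diary use at Visit 2, and no text says that the phone prompts are switched off on removal.
- **Rate.** Three of 33 (9%) would use almost all of the 10% dropout expected from every cause, and Section 4.2 excludes uncontrolled or unstable blood pressure.

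What does not stand is the inference that the diary is therefore secured. Requesting one visit, promising effort, and reviewing logs at a visit do not clearly instruct a subject who has been removed from the study to keep scoring pain every day. A mixed model without imputation is conventional, but it does not check its own missing-data assumption.

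**Conclusion.** The point holds as a cheap improvement with a small expected effect. As written, the blood-pressure rules end study participation where stopping the drug would serve the same safety purpose. They can therefore lose months 4-6 data that the protocol says it will analyse by intention to treat. The ambiguous timing of Visit 8 adds to this.

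The shift of 0.09 to 0.27 days rests on an assumed 1 to 3 removals of 33, all in the erenumab arm, with complete loss of a 3.0-day benefit.

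A reader might infer a bias in favour of erenumab. The documents do not establish a direction: placebo subjects can meet the same thresholds, and a removed subject may start an antihypertensive of a class that Section 4.2 lists as a migraine preventive. Nor do they support a threat to the result: at the planned effect, the conclusion would not change.

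**What to change.** Keep every stopping threshold and referral, and change the following:

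- **Section 3.2.2:** replace removal from the study, in both rules, with *discontinued from study drug; the phone diary continues to Day 180 unless consent is withdrawn*.
- **Sections 3.2.4 and 6.2:** state that Visit 8 for stopped subjects is at Day 180. Add no other visits.
- **Section 8.4.2:** state that diary data recorded after stopping enter the primary model under the randomized arm.
- **Data collection:** record any antihypertensive started.
- **Sensitivity analysis:** add one for months 4-6 data still missing from any cause, either delta-adjusted (for example 1, 2 and 3 days in the erenumab arm) or reference-based.

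Removal after emergency unblinding (Section 7.3.8) is a separate matter. Whether scores recorded after unblinding are used is for the sponsor to decide.

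The cost is an amendment, consent wording, one extra analysis, and some reminder calls and log reviews for a few subjects. The phone diary already exists. Some stopped subjects will not complete it, and later scores may reflect a new antihypertensive. The wording should be settled before subjects are removed, because daily scores not collected at the time cannot be recovered.

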3.2.4 FOLLOW-UP/END OF STUDY VISIT (VISIT 8)

Subjects will be asked to return for follow-up one month after the last study drug administration and undergo assessments and procedures listed in the schedule of events in section 1.3. Daily symptom and rescue medication data logs will be reviewed, and questionnaires completed. However, the study drug/placebo will not be administered.

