1.2 SCHEMA

1.3 SCHEDULE OF EVENTS (SOE)

Procedures	Screening / Lead-in Period	Baseline / Randomization & Initial Treatment Visit	Treatment Visit	Treatment Visit	Treatment Visit	Treatment Visit	Treatment Visit	Follow-up / End of Study visit	Unscheduled Visit
	Visit 1	Visit 2	Visit 3	Visit 4	Visit 5	Visit 6	Visit 7	Visit 8	Unscheduled
	Day -30 to -1	Day 0 (+6 days)	Day 30 (+/- 6 days)	Day 60 (+/- 6 days)	Day 90 (+/- 6 days)	Day 120 (+/- 6 days)	Day 150 (+/- 6 days)	Day 180 (+/- 6 days)	N/A
Informed Consent	x								
Demographics	x								
Medical History	x								
Randomization		x							
Study drug Administration		x	x	x	x	x	x		
Concomitant medication review	x	x	x	x	x	x	x	x	x
Physical exam	x	x	x	x	x	x	x	x	x
Home BP Monitoring (BP checks daily x 7 days following first dose of drug administration, then weekly and when symptomatic throughout duration of study)									→
Sinus CT Scan ¹	x								
Pregnancy test ²	x	x	x	x	x	x	x		
Endoscopy ³	x								
Review subject pain and blood pressure diary compliance and instruct subject on daily use	x	x	x	x	x	x	x	x	x
Migraine Assessment Tool (MAT)	x								

Procedures	Screening / Lead-in Period	Baseline / Randomization & Initial Treatment Visit	Treatment Visit	Treatment Visit	Treatment Visit	Treatment Visit	Treatment Visit	Follow-up / End of Study visit	Unscheduled Visit
	Visit 1	Visit 2	Visit 3	Visit 4	Visit 5	Visit 6	Visit 7	Visit 8	Unscheduled
	Day -30 to -1	Day 0 (+6 days)	Day 30 (+/- 6 days)	Day 60 (+/- 6 days)	Day 90 (+/- 6 days)	Day 120 (+/- 6 days)	Day 150 (+/- 6 days)	Day 180 (+/- 6 days)	N/A
Sinonasal Outcome Test questionnaire (SNOT-22)	x				x			x	
Migraine Functional Impact questionnaire (MFIQ)	x				x			x	
Pain Location Diagram	x								
Adverse event review and evaluation	x	x	x	x	x	x	x	x	x
Subject Compensation (clincard)	x	x	x	x	x	x	x	x	

1 - Most recent Sinus CT scan obtained as SOC should be within 12 months of the screening visit. If > 12 months then repeat for study purposes if not clinically indicated.

2 - Serum pregnancy test at screening, then urine pregnancy test on subsequent visits

3 - Endoscopy at screening as standard of care (SOC). If not done as SOC within 3 months of the screening visit, then complete it as a research procedure and charged to the study. Repeat only as clinically indicated.

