3 STUDY DESIGN

3.1 OVERALL DESIGN

This is a Phase IV, randomized, double-blinded, placebo-controlled single center trial of erenumab versus placebo in patients with mid-facial pain or pressure without evidence of sinus disease. Sixty-six eligible subjects will be randomized in a 1:1 ratio to receive subcutaneous injections of either 140 mg erenumab or placebo every 30 days for 6 months (last injection at day 150), followed by a final follow-up visit at day 180.

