7.3.3 TIME PERIOD AND FREQUENCY FOR EVENT ASSESSMENT AND FOLLOW-UP

AE review and evaluation will occur at every study visit prior to drug administration once a month, including the final visit, which will be one month after the final medication dose is administered.

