7.3.4 ADVERSE EVENT REPORTING

AEs will be reported by the patient throughout the entire study period study, including during study visits. All AEs, regardless of seriousness, severity, or presumed relationship to study therapy, will be recorded using medical terminology in the source document and on the case report form (CRF). Whenever possible, diagnoses will be given when signs and symptoms are due to a common etiology (e.g., cough, runny nose, sneezing, sore throat, and head congestion should be reported as "upper respiratory infection"). Investigators will record on the CRF their opinion concerning the relationship of the AE to study therapy and/or device (pre-filled syringe).

Any non-serious AE that occurs after the dose of study drug will be documented on a CRF page and followed until resolution, stabilization, or the End-of-Study Visit at Day 180 (Visit 8). Any SAE that occurs after the dose of study drug (regardless of relationship to study drug) will be followed until the event resolves, stabilizes, or becomes non-serious. The description of the AE will include type of event, date and time of onset, date and time of resolution, blinded investigator-specified assessment of severity and relationship to study drug, time of resolution of the event, seriousness, any required treatment or evaluations, and outcome.

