9.1.2 DISCONTINUATION AND STUDY STOPPING RULES

Subjects will be given the opportunity to withdraw from the study at any time. Every effort will be made to obtain follow-up information. Subjects who discontinue prematurely will be asked to return for a final follow-up visit either in person or by phone.

In the event of serious adverse events felt to be possibly related to erenumab and occurring in more than 3 study patients, the study will stop enrollment and the FDA will be notified for review and feedback. A single patient death possibly related to erenumab will also stop the study.

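### Visit 8 has two timings that differ for early stoppers, so a SNOT-22 or MFIQ from about Day 30 to 150 could be entered as the 6-month value

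*Combined protocol and SAP*

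**What the plan says.** Several places tie the final visit to a study day. The schedule of events (Section 1.3) puts Visit 8 at Day 180 with 6 days either side. Section 3.1 describes dosing "every 30 days for 6 months (last injection at day 150), followed by a final follow-up visit at day 180". Section 3.5 ends the study at the last subject's Day 180 visit, and Section 7.3.4 refers to "the End-of-Study Visit at Day 180 (Visit 8").

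Two places tie it to the last dose. Section 3.2.4 says: "Subjects will be asked to return for follow-up one month after the last study drug administration". Section 7.3.3 (Time Period and Frequency for Event Assessment and Follow-Up) places adverse event review at every visit, "including the final visit, which will be one month after the final medication dose is administered".

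For subjects who stop early, Section 6.2 says: "All subjects who received at least one dose of study drug or placebo will be requested to complete Visit 8", whether or not they finished the study. Section 9.1.2 says: "Subjects who discontinue prematurely will be asked to return for a final follow-up visit either in person or by phone". Neither names a study day.

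In Section 1.3, SNOT-22 and MFIQ are collected at Visits 1, 5 and 8 only. Section 8.4.3 compares their change from baseline at months 1, 3 and 6, using the primary endpoint's method. That method (Section 8.4.2) is a linear mixed model with scheduled visit as the time term and no imputation. Sections 6.2 and 8.4.1 promise an intention-to-treat analysis, and Section 6.2 includes withdrawn subjects in it.

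**The concern.** For a subject who stops dosing early, the two anchors give different dates, and no section says which governs. Section 3.2.4 is the section devoted to Visit 8, so a coordinator could reasonably follow it. Section 8.4.1 also starts the primary analysis once the last subject reaches Day 180 or is discontinued, so discontinued subjects need not be awaited.

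The questionnaires look back two weeks (SNOT-22) and seven days (MFIQ). A form completed a month after the last dose describes that period, not month 6. If it enters the model under Visit 8, an early status stands in for the Day 180 status, and only in discontinuers. The effect could differ by arm: subjects may be removed for raised blood pressure (Sections 3.2.2 and 6.2), and Section 2.3.1 reports hypertension after the study drug.

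**Working it through.** **The plan's own figure.** Section 8.2 assumes a difference of 3.0 days, SD 3.5, two-sided 0.05 and 90% power. By the normal approximation, n = 2 × (1.960 + 1.282)² × 3.5² / 3.0² = 28.6, so 29 per group; 29 / 0.90 = 32.2, so 33 per group and 66 in all. This reproduces. It is used here only for the 66 subjects and the 10% dropout.

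**Day of Visit 8 on the dose-based reading.** Doses fall on Days 0, 30, 60, 90, 120 and 150, so after k doses the visit falls on Day 30(k − 1) + 30 = 30k.

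| Doses received | Last dose | Visit 8, dose-based | Days short of Day 180 |
|---|---|---|---|
| 1 | Day 0 | Day 30 | 150 |
| 2 | Day 30 | Day 60 | 120 |
| 3 | Day 60 | Day 90 | 90 |
| 4 | Day 90 | Day 120 | 60 |
| 5 | Day 120 | Day 150 | 30 |
| 6 | Day 150 | Day 180 | 0 |

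For six doses the windows also agree: a last dose on Day 144 to 156 plus 30 gives Day 174 to 186, the Visit 8 window. After three doses the visit falls on the nominal day of Visit 5; after one or two it precedes Visit 5.

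**Number affected.** 0.10 × 66 = 6.6, about 3 per arm. This is a ceiling at that rate, because the 10% in Section 6.3 includes loss to follow-up, and those subjects may supply no Visit 8.

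**Illustrative size.** Assumptions not in the documents: a SNOT-22 difference D = 9 in subjects who complete dosing (9 is the minimal important difference cited in Section 8.4.3); the same share q of discontinuers in each arm; among them, a fraction e of D present at the early visit and a fraction r at Day 180.

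- Using early forms as month 6: D(1 − q + qe)
- True Day 180 difference: D(1 − q + qr)
- Distortion: Dq(e − r)

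| q | e | r | With early forms | True Day 180 | Distortion |
|---|---|---|---|---|---|
| 10% | 1 | 0 | 9.0 | 8.1 | +0.9 |
| 10% | 1 | 0.5 | 9.0 | 8.55 | +0.45 |
| 10% | 1 | 1 | 9.0 | 9.0 | 0 |
| 10% | 0.5 | 1 | 8.55 | 9.0 | −0.45 |
| 10% | 0 | 1 | 8.1 | 9.0 | −0.9 |
| 5% | 1 | 0 | 9.0 | 8.55 | +0.45 |
| 20% | 1 | 0 | 9.0 | 7.2 | +1.8 |

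The difference is overstated when the early visit shows more effect than remains at Day 180 (e > r) and attenuated when it shows less (e < r). If dropout differs by arm, changes over time within each arm no longer cancel and either direction is possible.

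**Scale.** With an assumed change-score SD of 15 to 25 (not in the documents), the standard error at 33 per arm is SD × √(2/33), or 3.7 to 6.2 points. A distortion of 0.9 is under a quarter of that.

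**The case against.** A reading without conflict is available. Section 3.2.4 follows the section on Visits 3 to 7, describes the planned course and refers back to the schedule. Read with Section 3.1, the last administration is the Day 150 dose, and Section 6.2 then asks withdrawn subjects for the Day 180 visit. The phrase in Section 9.1.2 for the closing visit matches the one that Section 3.1 places at Day 180. This stands as one possible reading. It does not settle the matter, because nothing says it prevails, Section 7.3.3 repeats the dose-based timing, and Section 8.4.1 allows analysis without waiting for discontinued subjects.

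A reader might infer that the plan says early forms are analysed as month 6. It does not. A model keyed to scheduled visit could equally leave out a Day 30 form, since none is scheduled then. The month-6 label is a risk created by the missing rule.

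A reader might also infer an 11% overstatement (9.0 / 8.1 = 1.11). That needs full effect at every early visit, even after one dose, and none at Day 180, even after five. With half the effect remaining it is about 5% (9.0 / 8.55 = 1.05), and the sign can reverse.

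Finally, relabelling alone is not a cure. If the Day 180 form is missing, the mixed model under missing at random predicts it largely from subjects still on treatment, which gives roughly the same 9.0. That objection stands, and it is why the questionnaires need to be collected at Day 180.

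**Conclusion.** The documents contradict themselves on when Visit 8 takes place for a subject who stops early. Following Section 3.2.4 as written can put a form from about Day 30 to 150 where the 6-month SNOT-22 or MFIQ belongs. The consequence is confined to those two secondary endpoints at that time point. The documents do not support extending it to the primary endpoint, which comes from the daily diary.

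At most about 6 or 7 of 66 subjects are affected at 10% dropout. With equal dropout and a 9-point SNOT-22 difference, the overstatement is 0 to 0.9 points if the early visit shows full effect, and the difference may be attenuated if it does not. These sizes rest on the stated assumptions; the date conflict does not. The effect is modest, but a status not recorded at Day 180 cannot be recovered later, so it is worth correcting.

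**What to change.** 1. Reconcile Sections 1.3, 3.1, 3.2.4, 6.2, 7.3.3 (timing of event assessment), 7.3.4 and 9.1.2 on when Visit 8 occurs for a subject who stops early. The timing of safety follow-up after the last dose is for the sponsor to settle.
2. Separately, for the efficacy questionnaires, request SNOT-22 and MFIQ at Day 180 ± 6 from every randomised subject who has not withdrawn consent. Both are self-administered, and Section 9.1.3 already describes secure survey links sent to the subject's phone, so this can be done remotely.
3. Code any earlier closing visit as early termination. Assign its questionnaires to an analysis time point only if the actual study day falls within a pre-specified window: Day 174 to 186 for month 6 and, following the Visit 5 window, Day 84 to 96 for month 3. A Day 150 form would then be listed but not analysed as month 6.

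The cost is protocol wording, one visit code and at most about 6 or 7 remote completions at the planned dropout. The sample size is unchanged. Some withdrawn subjects will decline; their month-6 value will be missing and rest on the missing-at-random assumption, so the bias is not removed for them. The number should be reported by arm.
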